**Brentuximab vedotin (ADCETRIS®)**  
**Clinical Study Protocol C25003 Amendment 7, EudraCT: 2011-005450-60**

**Table 7-1 Pharmacokinetic Sampling Time Points**

Cycle	Study Day	Time	Window	Relative Time
Full A+AVD Arm				
1-6	1	Predose	Within prior 4 hr	Start of brentuximab vedotin infusion
		EOI (~30 min)	Within 1 hour post EOI	End of brentuximab vedotin infusion
	15	Predose	Within prior 4 hr	Start of brentuximab vedotin infusion
		EOI (~30 min)	Within 1 hour post EOI	End of brentuximab vedotin infusion
1 and 3, in addition	2	24 hr	±4 hr	Start of brentuximab vedotin infusion
	3	48 hr	±4 hr	Start of brentuximab vedotin infusion
Additional Sampling for 50-Patient Subset of A+AVD Arm				
1 and 3	1	2 min	±2 min	End of doxorubicin infusion
		2 min	±2 min	End of vinblastine infusion
		2 min	±2 min	End of dacarbazine infusion
		1 hr	±5 min	End of brentuximab vedotin infusion
		6 hr	±10 min	End of brentuximab vedotin infusion
	8	168 hr	±24 hr	End of brentuximab vedotin infusion
Additional Sampling for 50-Patient Subset of ABVD Arm				
1 and 3	1	Predose	Within prior 4 hr	Start of doxorubicin infusion
		2 min	±2 min	End of doxorubicin infusion
		2 min	±2 min	End of vinblastine infusion
		2 min	±2 min	End of dacarbazine infusion
		1 hr	±5 min	End of dacarbazine infusion
		6 hr	±10 min	End of dacarbazine infusion
	2	24 hr	±4 hr	End of dacarbazine infusion
	8	168 hr	±24 hr	End of dacarbazine infusion

Abbreviations: A+AVD=brentuximab vedotin (ADCETRIS®) plus doxorubicin, vinblastine, and dacarbazine; ABVD=doxorubicin, bleomycin, vinblastine, and dacarbazine; EOI=end of infusion; hr=hour; min=minutes.

The 50 patients in each treatment arm from whom additional PK samples are obtained will be recruited from sites that agree to participate. Further, approximately 20 patients in each 50-patient intensive-sampling group must be Asian.

#### **7.4.20 Serum Biomarkers**

Blood for serum samples will be collected as specified in the [Schedule of Events](#) to measure circulating biomarkers such as soluble CD30 (sCD30), thymus- and activation-regulated chemokine (TARC), cutaneous T-cell-attracting chemokine (CTACK), and interleukin-6 (IL-6). Previous research has demonstrated a relationship between circulating sCD30 concentration and overall tumor burden. A decrease in sCD30 may reflect a decrease in overall tumor burden. The Reed-Sternberg cells characteristic of classical HL produce high concentrations of TARC that correlate with increased T-cell infiltration of tumor tissue.

Further, previous phase 2 clinical studies of brentuximab vedotin showed CCI

[REDACTED]

Biomarkers such as sCD30, TARC, and IL-6 may be measured on Day 1 of all cycles and at the EOT visit. Baseline values and changes in these markers may be compared to efficacy. In addition, the possible impact of sCD30 concentrations on PK will be explored.

The timing of the blood samples may be changed and/or the number of samples reduced if emerging data indicate that changes to the sampling scheme are needed to better characterize the effects of brentuximab vedotin. Details regarding the preparation, handling, and shipping of samples are provided in the Study Manual.

#### **7.4.21 Immunogenicity Measurements**

Blood for serum samples will be collected as specified in the [Schedule of Events](#) to evaluate antitherapeutic antibody (ATA) and neutralizing ATA as a PK and safety assessment. On dosing days, the blood samples for ATA and neutralizing ATA assessment must be collected before dosing. Neutralizing ATA assessment will be performed only for ATA-positive samples. Immunogenicity parameters will be assayed only for patients who receive at least 1 brentuximab vedotin dose.

#### **7.4.22 Germline DNA Polymorphism Assessment**

For patients on the A+AVD arm only, an optional blood sample will be collected on Day 1 of Cycle 1, before dosing, to examine genotyping variations in the germ line genes of the disease pathway, drug mechanism, and drug clearance proteins, such as CD30, tubulin, Fcneo, and Fcγ receptors.

#### **7.4.23 Fertility Assessment**

The incidence of pregnancy in each treatment arm will be assessed at the time of study closure. Any pregnancy occurring in patients or their partners from the date of first dose until the date of study closure should be reported.

#### **7.5 Completion of Treatment**

Patients will be considered to have completed study treatment if they:

- Complete frontline treatment (see [Table 8-1](#)), or
- Experience PD or die prior to completion of frontline treatment

#### **7.6 Completion of Study**

Patients will be considered to have completed the study if they meet both of the following criteria:

- Complete 6 cycles of frontline treatment
- Have 5 years of follow-up or have died

Regardless of the duration of treatment, all patients will remain on study for follow-up following the last dose of study treatment until they withdraw consent for further follow-up, are lost to follow-up, have been followed for 5 years from randomization, or until study closure. The study is expected to close approximately 7 years after the first patient starts study treatment. Posttreatment follow-up is further described in [Section 7.10](#).

For patients who do not complete 6 treatment cycles, please see the [Schedule of Events](#) for details of follow-up assessments.

#### **7.7 Discontinuation of Treatment With Study Drug, and Patient Replacement**

Study drug must be permanently discontinued for patients meeting any of the following criteria:

- Completed 6 cycles of A+AVD or ABVD
- Investigator deems it is in the patient's best interest to discontinue

The primary reason for study treatment withdrawal must be documented.

**Brentuximab vedotin (ADCETRIS®)**

**Clinical Study Protocol C25003 Amendment 7, EudraCT: 2011-005450-60**

Patients who discontinue from study treatment will remain on study for follow-up unless they withdraw consent for the follow-up phase of the study. All randomized patients will be followed until study closure (see Section 7.6).

Patients who are randomized to a treatment arm but do not receive study drug for any reason will not be replaced.

Treatment with study drug may also be discontinued for any of the following reasons:

- AE
- Protocol violation
- PD
- Unsatisfactory therapeutic response
- Study terminated by sponsor
- Withdrawal by subject
- Lost to follow-up
- Other

Once study drug has been discontinued, all study procedures outlined for the EOT visit will be completed as specified in the [Schedule of Events](#). The primary reason for study drug discontinuation will be recorded on the eCRF.

Note that some patients may discontinue study drug for reasons other than PD before completing the full treatment course (eg, after Cycle 2 based on a Deauville score of 5); these patients will remain in the study for posttreatment assessments as outlined in the [Schedule of Events](#) until disease progression occurs.

## **7.8 Withdrawal of Patients From Study**

A patient may be discontinued from the study (during treatment cycle or follow-up) for any of the following reasons:

- Lost to follow-up
- Study terminated by sponsor
- Withdrawal by subject
- Death
- Other

The consequence of study withdrawal is that no new information will be collected from the withdrawn patient and added to the existing data or any database.

Millennium or their designee must be notified in writing if a patient is withdrawn from study treatment or from the study. The reason(s) for withdrawal must be documented in the patient's medical records. The investigators will make every reasonable effort to keep each patient on the study until all planned treatments and assessments have been performed. If a patient withdraws from study treatment, every attempt should be made to follow the patient until death or administrative study closure. Final treatment assessments will be performed before any other therapeutic intervention if possible. Additionally, any planned alternative treatments should be documented on the patient's medical records and CRF.

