## **Brentuximab vedotin (ADCETRIS®)**

### **Clinical Study Protocol C25003 Amendment 7, EudraCT: 2011-005450-60**

every 6 months until the first of disease progression or study closure. CT scans are required every 12 weeks ( $\pm 1$  week) until 12 months of PTFU and then every 6 months ( $\pm 2$  weeks) until study closure. For patients who have PD, survival/disease status and information regarding the initiation of an alternative lymphoma treatment may be obtained by phone call. To support fertility assessment, any pregnancy occurring in patients or their partners from the date of first dose until the date of study closure should be reported.

Patients who stop treatment for any reason other than PD will continue to have mPFS follow-up visits until the occurrence of PD; the patient withdraws consent for further follow-up; or, the start of another anticancer therapy for patients not in CR after completion of frontline therapy.

Patients will be followed for survival until 5 years from the date of the last patient randomized, or death, whichever occurs first. Survivor information may be collected by methods that include, but are not limited to, telephone, e-mail, mail, or retrieved from online or other databases (eg, social security indexes). In addition, the start of another anticancer therapy will be collected.

See the [Schedule of Events](#) for appropriate assessments during follow-up.

NOTE: Related SAEs must be reported to the Millennium Department of Pharmacovigilance & Risk Management or designee. This includes deaths that the investigator considers related to study drug that occur during the posttreatment follow-up. Refer to Section 10 for details regarding definitions, documentation, and reporting of SAEs.

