#### **Overall Survival**

OS is defined as the time from the date of randomization to the date of death. Patients without documented death at the time of analysis will be censored at the date last known to be alive.

Two formal analyses will be performed for OS. An OS interim analysis will be performed at the time of the final mPFS analysis, and the final analysis of OS will be performed when 112 deaths have occurred, assuming 5-year OS rates for the A+AVD and ABVD arms are 91% and 88%, respectively (HR=0.75). Overall type I error will be controlled using the O'Brien-Fleming method with a Lan-DeMets alpha-spending function.

Stratified log-rank testing will be used to compare OS between the 2 treatment arms. The hazard ratios along with the 95% CIs will be estimated using a stratified Cox regression model. The Kaplan-Meier method will be used to estimate the distribution of the OS endpoint for each treatment. Median survival times (if estimable), along with the 2-sided 95% CIs will be presented. Analysis of OS will be performed based on the ITT population.

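### Protocol 7.8 does not separate loss to follow-up from withdrawal of consent when it stops data collection, which sits badly with the survival follow-up in 7.10 and may leave some obtainable deaths out of OS

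*Protocol*

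**What the plan says.** Protocol 7.8 opens its list with "A patient may be discontinued from the study (during treatment cycle or follow-up) for any of the following reasons". The list contains loss to follow-up, termination by the sponsor, withdrawal by the subject, death and a catch-all category. One consequence follows, not divided by reason: "The consequence of study withdrawal is that no new information will be collected from the withdrawn patient". The same sentence extends this to adding anything to the data already held or to any database. The section then uses the word withdrawal for the list as a whole: "The reason(s) for withdrawal must be documented in the patient's medical records". Its later request to follow patients until death concerns those who withdraw from study treatment, not from the study.

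Protocol 7.6 keeps patients on study "until they withdraw consent for further follow-up, are lost to follow-up, have been followed for 5 years from randomization, or until study closure", so loss of contact ends time on study there too.

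Protocol 7.10 sets survival follow-up to death or 5 years after the last randomization, with no exception for lost patients, and adds: "Survivor information may be collected by methods that include, but are not limited to, telephone, e-mail, mail, or retrieved from online or other databases". Section 7.7 says that all randomized patients are followed to study closure, with a cross-reference to 7.6.

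For OS, protocol 8.1.6.2 says: "Patients without documented death at the time of analysis will be censored at the date last known to be alive". SAP 5.8.3 repeats this rule and does not discuss deaths found after a patient is lost. SAP 5.4.5, on withdrawals and losses, says only that patients are not replaced.

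**The concern.** A patient who cannot be reached has not refused further data. A public-records search is most useful for exactly that patient, yet a site applying 7.8 literally could close the patient out and add nothing more, while a site applying 7.10 would search and record the death. Both would be following the protocol. With about 250 centers, practice could vary.

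OS is the only endpoint tested formally after modified progression-free survival (mPFS), and its final analysis rests on 112 deaths. The stratified log-rank test and Cox model assume that censoring carries no information about prognosis. Patients who disappear after relapse or toxicity may not be typical, and in an open-label trial the rate of loss may differ by arm. Waiting for more deaths does not remove a bias of that kind.

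**Working it through.** **The text.** Three readings of 7.8 were compared for a lost patient whose death later appears in a public index.

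- Literal: the patient is withdrawn, nothing is added, and OS is censored at the date last known alive. This conflicts with 7.10.
- Narrow: only data supplied by the patient are barred, so the death counts. This agrees with 7.10, but 7.8 does not say so, and its sentence goes on to mention adding to any database.
- Optional: the patient need not be discontinued at all, so 7.10 applies. This agrees with 7.10 but leaves the choice to the site.

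The outcome depends on which reading a site adopts.

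**Inputs.** 5-year OS of 91% (A+AVD) and 88% (ABVD), and the 112-death trigger (protocol 8.1.6.2); 620 per arm (4.2); 36 months of accrual (8.1.1), taken as uniform; interim at the final mPFS analysis, about 2 years after the last patient, and final OS at about 4 years (Protocol Summary). The 5% annual dropout in 8.1.1 belongs to the mPFS calculation. No rate is given for OS, so 0 to 5% is an assumed range.

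**The plan's figures.** The OS rates give HR = ln(0.91)/ln(0.88) = 0.738 under constant hazards, against 0.75 stated. As a check of the power formula, 260 mPFS events at HR 0.67 give z = (√260/2) × |ln 0.67| − 1.96 = 1.27, or 89.8%, against 90% stated.

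**Expected recorded deaths.** Death hazards per year are λ = −ln(0.91)/5 = 0.01886 and −ln(0.88)/5 = 0.02557. The loss hazard is η = −ln(1 − annual loss), which is 0.05129 at 5%. With h = λ + η and F years of follow-up after the last patient,

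deaths per arm = 620 × (λ/h) × [1 − (e^(−hF) − e^(−h(F+3)))/(3h)].

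ABVD at F = 4:
- No loss: 620 × [1 − (0.9028 − 0.8361)/0.0767] = 81.2.
- 5% loss: h = 0.07686, and 620 × 0.3326 × [1 − (0.7353 − 0.5839)/0.2306] = 70.8.

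A+AVD gives 61.0 and 53.2 in the same way. The totals are 142.2 and 124.0.

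| Assumed annual loss, none captured | Deaths at 2 years (interim) | Deaths at 4 years | Fall at 4 years | 112th death, years after last patient |
|---|---|---|---|---|
| 0% | 92.5 | 142.2 | – | 2.77 |
| 1% | 90.8 | 138.4 | 2.7% | 2.88 |
| 2% | 89.1 | 134.6 | 5.3% | 2.98 |
| 5% | 84.3 | 124.0 | 12.8% | 3.36 |

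The largest delay is 3.36 − 2.77 = 0.59 years. If instead no deaths occur after year 5, which the documents do not state, deaths at 4 years fall from 126.1 to 111.9 at 5% loss (11.3%). The 112th death then moves from 2.91 to 4.02 years, a delay of 1.1 years.

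**Power.** At 112 deaths and HR 0.75, z = (√112/2) × |ln 0.75| − 1.96 = −0.44, or 33.1% (fixed-sample). It depends on the number of deaths, not on how long they take, so it is the same in every row.

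**The case against.** The strongest reply is that the sections can be followed together. Section 7.8 speaks of information collected from the patient, and a death index is not that. Its list includes death, for which a bar on new information has no sensible meaning; this suggests a set of disposition categories, with the consequence aimed at real withdrawal. Discontinuation is optional, 7.8 asks for every reasonable effort to keep patients on study, and 7.10 already names the search methods. The cross-reference from 7.7 to 7.6 also softens that part of the conflict.

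Much of this stands. A reader might infer that 7.8 forbids any new information about lost patients, or that their deaths are discarded from OS. The documents do not support either. The OS rules censor only patients without a documented death and place no limit on the source of the documentation, and SAP 5.11.1.3 summarizes all deaths on study and during follow-up.

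What does not stand is that no change is needed. The compatible reading has to be supplied by the reader. The searches in 7.10 are as optional as the discontinuation in 7.8, whereas the consequence in 7.8 is stated without condition.

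On size, the objection is right that 5% is a ceiling. It borrows the mPFS dropout rate, treats all dropout as loss whose deaths could otherwise be found, and ignores consent withdrawals and countries where searches are not allowed. In the scenario with no deaths after year 5, 112 deaths with 5% loss fall at 4.02 years, close to the planned 4 years. The planned timing may therefore already absorb such a loss.

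**Conclusion.** The point holds as an inconsistency that can lose deaths from OS, not as a rule that certainly does. Sections 7.8 and 7.6 treat loss of contact like withdrawal of consent; 7.10, and less directly 7.7, do not.

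The size is unknown because the documents give no OS loss rate. The table gives an upper bound for each assumed rate, under constant hazards, uniform accrual and loss unrelated to prognosis. At 1 to 2% annual loss the shortfall at 4 years is about 3 to 5%; the 13% at 5% loss should not be read as the expected effect. The 1.1-year delay applies only if deaths stop after year 5.

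A reader might also infer a loss of power for final OS. That is not so, because the analysis waits for 112 deaths. What remains is a later final analysis, up to about 8 fewer deaths at the interim, and possible bias. The bias cannot be sized from the documents, and nothing in them shows that loss would differ by arm.

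**What to change.** In protocol 7.8, and correspondingly in 7.6, limit the bar on new data to patients who withdraw consent for further data collection. State that vital status of patients lost to follow-up or otherwise discontinued continues to be sought by the 7.10 methods, where local law and consent permit. Require a vital-status check before each of the two OS data cuts, and say in SAP 5.8.3 that deaths found this way count in OS. Reporting the number lost, by arm, with each OS analysis would let readers judge the risk of bias.

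The cost is a few sentences of text and some site and database checking before two data cuts. Searches will not be possible in every country, so some loss will remain. Patients who withdraw consent stay protected.

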## **7.9 Study Compliance**

Study drug will be administered or dispensed only to eligible patients under the supervision of the investigator or identified subinvestigator(s). The appropriate study personnel will maintain records of study drug receipt and dispensing.

## **7.10 Posttreatment Follow-up Assessments**

Posttreatment follow-up for all patients consists of a physical exam, B symptom assessment, selected QOL assessments as specified in the [Schedule of Events](#), medical resource utilization, CT scan, and collection of survival/disease status and anticancer treatment for HL. Information regarding new primary malignancies will be recorded. All assessments except CT scans are to be performed every 3 months until 36 months after the EOT and then

## **Brentuximab vedotin (ADCETRIS®)**

### **Clinical Study Protocol C25003 Amendment 7, EudraCT: 2011-005450-60**

every 6 months until the first of disease progression or study closure. CT scans are required every 12 weeks ( $\pm 1$  week) until 12 months of PTFU and then every 6 months ( $\pm 2$  weeks) until study closure. For patients who have PD, survival/disease status and information regarding the initiation of an alternative lymphoma treatment may be obtained by phone call. To support fertility assessment, any pregnancy occurring in patients or their partners from the date of first dose until the date of study closure should be reported.

Patients who stop treatment for any reason other than PD will continue to have mPFS follow-up visits until the occurrence of PD; the patient withdraws consent for further follow-up; or, the start of another anticancer therapy for patients not in CR after completion of frontline therapy.

Patients will be followed for survival until 5 years from the date of the last patient randomized, or death, whichever occurs first. Survivor information may be collected by methods that include, but are not limited to, telephone, e-mail, mail, or retrieved from online or other databases (eg, social security indexes). In addition, the start of another anticancer therapy will be collected.

See the [Schedule of Events](#) for appropriate assessments during follow-up.

NOTE: Related SAEs must be reported to the Millennium Department of Pharmacovigilance & Risk Management or designee. This includes deaths that the investigator considers related to study drug that occur during the posttreatment follow-up. Refer to Section 10 for details regarding definitions, documentation, and reporting of SAEs.

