**Brentuximab vedotin (ADCETRIS®)**  
**Clinical Study Protocol C25003 Amendment 7, EudraCT: 2011-005450-60**

	Day (D)	Screening -28 to D1	Enrollment Within 24 hours of first dose	Cycle (C) Every 28 Days																		EOT	PTFU a Every 3 months for 36 months and then every 6 months until study closure
				Cycle 1				Cycle 2			Cycle 3				Cycle 4		Cycle 5		Cycle 6				
				D1	D2	D3	D 15	D1	D 15	D 25	D1	D2	D3	D 15	D1	D 15	D1	D 15	D1	D 15	D1		
PK/PD	PK Sample o			X	X	X	X	X	X		X	X	X	X	X	X	X	X	X	X			
	Serum biomarkers such as CCI CCI																						
	Immunogenicity d			X			X				X				X		X			X		X	
	Germline DNA f			X																			

Abbreviations: ATA=antitherapeutic antibodies; A+AVD=brentuximab vedotin (ADCETRIS®) plus doxorubicin, vinblastine and dacarbazine; ABVD=doxorubicin, bleomycin, vinblastine, and dacarbazine; BSA=body surface area; CT=computed tomography; CTACK=cutaneous T-cell-attracting chemokine; ECG=electrocardiogram; ECOG=Eastern Cooperative Oncology Group; EOI=end of infusion; EOT=end of treatment; FDG=fluorodeoxyglucose; IL-6=interleukin-6; IPFP=International Prognostic Factor Project; PD=pharmacodynamics; PET=positron emission tomography; PK=pharmacokinetics; PTFU=posttreatment follow-up; TARC=thymus and activation-regulated chemokine.

Tests and procedures should be performed on schedule, but occasional changes are allowable (±3 days) for logistic reasons unless indicated otherwise.

- a. All treated patients will be followed for progression-free survival disease status, event-free survival and overall survival every 12 weeks (±1 week) until 36 months of PTFU and then every 6 months until study closure. For patients who have progressive disease, survival/disease status and information regarding the initiation of an alternative lymphoma treatment may be obtained by phone call. Note: Radiological assessments are only required every 12 weeks (±1 week) until 12 months of PTFU and then every 6 months until study closure. To assist with scheduling of visits, patients may begin to align the timing of their follow-up visits with the timing of the CT scans during PTFU, when applicable.

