**Brentuximab vedotin (ADCETRIS®)**

**Clinical Study Protocol C25003 Amendment 7, EudraCT: 2011-005450-60**

have experienced a prior infusion-related reaction should be premedicated according to institutional guidelines for subsequent infusions. Premedication may include acetaminophen, an antihistamine and a corticosteroid.

Clinically significant laboratory abnormalities were to be reported as adverse events per the phase 2 study protocols. Central laboratory data were collected only predose for each treatment cycle. Few patients overall had postbaseline worsening to Grade 3 or higher in clinical laboratory values. The clinical laboratory parameters for which the most patients had new or worsening shifts to  $\geq$ Grade 3 were low neutrophils (11%), lymphocytes (11%), platelets (6%), leukocytes (5%), and high glucose (6%). Only 1 patient in the phase 2 studies had Grade 3 ALT and AST.

Any treatment that can decrease immune function may contribute to malignancy and infections; patients are to be monitored for these events during the treatment period and up to and including 30 days after the last dose of frontline therapy.

Complete blood counts should be monitored prior to each dose of brentuximab vedotin and more frequent monitoring should be considered for patients with Grade 3 or 4 neutropenia. Prolonged ( $\geq$ 1 week) severe neutropenia can occur. If Grade 3 or 4 neutropenia develops, manage by dose delays, reductions, or discontinuations (see [Table 6-1](#)).

Tumor lysis syndrome may occur. Patients with rapidly proliferating tumor and high tumor burden are at risk of tumor lysis syndrome and should be closely monitored. If tumor lysis syndrome occurs, take medically appropriate measures.

Stevens-Johnson syndrome has been reported with brentuximab vedotin. If Stevens-Johnson syndrome occurs, brentuximab vedotin must be discontinued and the appropriate medical therapy administered.

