### **10.3 Monitoring of Adverse Events and Period of Observation**

AEs, both nonserious and serious (which include all deaths), will be monitored throughout the study as follows:

- AEs will be reported from first dose of frontline therapy through 30 days after administration of the last dose of frontline therapy and recorded in the eCRFs. A diagnosis of a malignancy other than classical HL that occurs at any time prior to study closure must be recorded in the eCRF regardless of causality. Additionally, events of malignancy occurring more than 30 days post the last dose of frontline therapy that are deemed serious and related to study drug must be reported to Millennium Department of Pharmacovigilance & Risk Management or designee on an SAE form. All events relating to peripheral neuropathy, regardless of seriousness, will be followed for all changes in severity until resolution to baseline or study closure, whichever occurs first, and recorded in the eCRF.

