## **Brentuximab vedotin (ADCETRIS®)**

### **Clinical Study Protocol C25003 Amendment 7, EudraCT: 2011-005450-60**

- Treatment-related AEs will be reported from first dose of frontline therapy through 30 days after administration of the last dose of frontline therapy and recorded in the eCRFs. Treatment-related AEs must be monitored for resolution through event resolution or study closure.
- Serious pretreatment events will be reported to Millennium Department of Pharmacovigilance & Risk Management or designee from the time of the signing of the ICF up to first dose of frontline therapy, but will not be recorded in the eCRF.
- Related and unrelated SAEs will be reported to Millennium Department of Pharmacovigilance & Risk Management or designee from the first dose of frontline therapy through 30 days after administration of the last dose of frontline therapy and recorded in the eCRF. All SAEs should be monitored until they are resolved or are clearly determined to be due to a patient's stable or chronic condition or intercurrent illness(es). Any SAE that occurs between 30 days post last dose of frontline therapy and study closure that the investigator considers related to study drug must be reported to the Millennium Department of Pharmacovigilance & Risk Management or designee. In addition, events of PML must be reported on an SAE form, regardless of treatment arm or causal relationship, from the first dose of study drug through death or termination of the study by the sponsor.

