5.11.1 Adverse Events

Treatment-emergent adverse events are defined as any AE that occurs after administration of the first dose of study drug and through 30 days after the last dose of frontline therapy.

The MedDRA dictionary will be used to code the investigator's adverse event terms.

Adverse event tables will summarize subject incidence by treatment group actually received.

The severity of adverse events will be assessed using NCI CTCAE version 4.03.

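### New malignancies must be recorded to study closure, but Sections 1.5 and 7.10 give shorter windows, no post-progression contact asks about late harms, and the SAP plans no by-arm summary of non-fatal late malignancy or neuropathy resolution

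*Protocol*

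**What the plan says.** **Malignancy.** Protocol Section 10.3: "A diagnosis of a malignancy other than classical HL that occurs at any time prior to study closure must be recorded in the eCRF", whether or not related. Section 1.5, which concerns infections as well as malignancy, says: "patients are to be monitored for these events during the treatment period and up to and including 30 days after the last dose"; the dose meant is the final one of frontline treatment. Section 7.10 says that new primary malignancies will be recorded. It then ends every assessment except CT at a common point, 3-monthly for 36 months and then "every 6 months until the first of disease progression or study closure". For patients with progressive disease, Section 7.10 and Schedule of Events footnote a both say: "survival/disease status and information regarding the initiation of an alternative lymphoma treatment may be obtained by phone call".

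**Neuropathy.** Section 10.3 wants all neuropathy events "followed for all changes in severity until resolution to baseline or study closure, whichever occurs first, and recorded in the eCRF". The adverse event row of the Schedule of Events agrees.

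**PML.** Section 10.3: "events of PML must be reported on an SAE form, regardless of treatment arm or causal relationship", and this runs "from the first dose of study drug through death or termination of the study by the sponsor".

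Section 7.4.9 refers to Section 10 for all three items.

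**Analysis.** SAP 5.11.1 defines treatment-emergent events thus: "any AE that occurs after administration of the first dose of study drug and through 30 days after the last dose of frontline therapy". Both the incidence tables in 5.11.1.1 and the SAE tables in 5.11.1.2 use that definition, and the intensity summary counts a repeated event once, at its maximum grade. Two outputs go further: a by-subject listing of all SAEs (5.11.1.2) and a summary of all deaths with cause, including those in follow-up (5.11.1.3).

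**The concern.** The protocol gives three end points for malignancy: 30 days after last dose, progression, and study closure. A site that works from Section 7.10 and the Schedule of Events has no prompt after progression. The Schedule has no row for malignancy or PML, and its SAE row stops at 30 days. Section 7.10 carries pregnancy reporting explicitly to study closure but does not say the same of malignancy. For neuropathy and PML the duty to record is clear, yet nothing says at which post-progression contact anyone asks.

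Progression is part of the outcome expected to differ between arms, so a stop at progression would make observation time for late harm differ by arm. The patients affected are also those likely to receive further treatment, including radiation, which Section 1.4 links to later malignancy.

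The analysis gap does not depend on how Section 7.10 is read. After 30 days, an SAE report is required only for related SAEs and for PML. A late, non-fatal malignancy judged unrelated therefore goes into the eCRF but into neither the SAE listing nor any specified table. Neuropathy grade changes recorded to closure have no planned summary either. Yet the safety objective is comparative, A+AVD relative to ABVD.

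**Working it through.** **1. The plan's own figure.** Inputs from Protocol 8.1.1 and SAP 5.1: 2-year mPFS 81% v 73%, HR 0.67, 260 events, 90% power, 1-sided 0.025.
- HR = ln 0.81 / ln 0.73 = 0.670.
- Schoenfeld events = 4(1.960 + 1.282)² / (ln 0.67)² = 263 after rounding up. Power at 260 events is 89.8%. The stated design is reproduced.

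**2. Patients reaching the stop by year 2**, ignoring dropout: 620 × 0.19 = 118 (A+AVD) and 620 × 0.27 = 167 (ABVD), a ratio of 1.42.

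**3. Hand check of observed time**, with everyone otherwise followed for 5 years and no deaths or dropout. Hazards are −ln 0.81 / 2 = 0.105 and −ln 0.73 / 2 = 0.157.
- No events after year 2: (1 − S)/λ + 3S = 0.19/0.105 + 3 × 0.81 = 4.23 years v 0.27/0.157 + 3 × 0.73 = 3.91 years.
- Half the hazard after year 2: 4.05 v 3.67 years.

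This check is crude because it treats time after death as available.

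**4. Fuller calculation.** From the plan: 620 per arm, 36 months of accrual (taken as uniform), 5% annual dropout, and 5-year OS of 91% v 88%. Closure is C = 4 or 5 years after the last patient, because Sections 4.3 and 7.10 differ. Assumptions not in the documents: the mPFS event stands for progression, OS is exponential, treatment ends at 0.5 year, and the hazard after year 2 is 0 to 1 times the earlier one.

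With d = −ln 0.95 and entry time e uniform on 0 to 3 years, averaged over e:
- alive follow-up = ∫ S_OS(t) exp(−dt) dt, from t = 0.5 to 3 + C − e
- covered follow-up = the same integral with min(S_mPFS, S_OS)
- uncovered share = 1 − covered / alive.

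| Hazard after year 2 | C | Covered / alive years, A+AVD | Covered / alive years, ABVD | Uncovered, A+AVD v ABVD | Ratio of covered shares |
|---|---|---|---|---|---|
| 0 | 4 | 3.568 / 4.055 | 3.262 / 3.977 | 12.0% v 18.0% | 1.073 |
| 0 | 5 | 4.164 / 4.713 | 3.799 / 4.609 | 11.7% v 17.6% | 1.072 |
| 0.25 | 4 | 3.462 / 4.055 | 3.121 / 3.977 | 14.6% v 21.5% | 1.088 |
| 0.25 | 5 | 3.999 / 4.713 | 3.581 / 4.609 | 15.2% v 22.3% | 1.092 |
| 0.5 | 4 | 3.362 / 4.055 | 2.994 / 3.977 | 17.1% v 24.7% | 1.101 |
| 0.5 | 5 | 3.847 / 4.713 | 3.388 / 4.609 | 18.4% v 26.5% | 1.110 |
| 1 | 4 | 3.182 / 4.055 | 2.773 / 3.977 | 21.5% v 30.3% | 1.125 |
| 1 | 5 | 3.577 / 4.713 | 3.064 / 4.609 | 24.1% v 33.5% | 1.142 |

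Uncovered person-years run from 302 v 444 (first row) to 705 v 958 (last row). The last column is the factor by which the stop alone would inflate the A+AVD:ABVD ratio of per-patient counts, if the late-event rate were equal in both arms and the same before and after progression. Collection to closure makes it 1.00.

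Expected mPFS events at 60 months are 272, 310, 347 and 412 for the four hazard assumptions. Against the plan's 260, and its assumption that the event rate falls after year 2, the upper rows fit the design best.

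**5. Reach of the SAP incidence tables.** The treatment-emergent window is about 0.5 + 30/365 = 0.58 year. Mean planned follow-up is C + 1.5 = 5.5 to 6.5 years, so the tables cover about 9-11% of it.

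**The case against.** The strongest reply is that Section 10.3 is the specific, mandatory rule and Section 7.4.9 makes it govern all three items. Section 1.5 is background risk text. In Section 7.10 the malignancy sentence stands outside the list of assessments and has no end date of its own. The progression stop cannot be exhaustive, since the list includes survival status, which the same section continues after progression. Permission to use the phone sets a mode of contact, not a limit on what is recorded. Section 7.7 follows all randomized patients to closure. This stands to the extent that under-collection cannot be stated as fact. It does not remove the conflicting text or supply a prompt.

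A reader might infer that Sections 1.5 and 7.10 also cut short neuropathy and PML recording. They do not: Section 1.5 names only malignancy and infections, and Section 7.10 sets no end date for the other two.

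A reader might also infer that the SAP looks at nothing after 30 days. It does: it tabulates all deaths with cause and lists all SAEs. Protocol 8.1.4 and SAP 5.4.1 promise in general terms that all available safety data will appear in listings and tabulations, and Protocol 8.1.9 allows further safety analyses. None of these specifies a by-arm summary of non-fatal late malignancy or neuropathy resolution.

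**Conclusion.** The point holds for malignancy as a conflict in the text, for neuropathy and PML as a missing prompt after progression, and for the SAP as a missing pair of by-arm summaries. If collection stopped at progression, about 12-24% v 18-34% of post-treatment follow-up would be uncovered, with an inflation factor of about 1.07 to 1.14. The lower end is closest to the plan's own event projection.

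The effect is modest. It also runs against A+AVD, so the documents do not support reading it as a bias that flatters the experimental arm. The range is not a strict bound. mPFS also counts treated non-complete responders, which overstates progression, while the hazard after year 2 is assumed. If treatment after progression raises the malignancy rate, more events would be missed than the person-time suggests.

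No number of neuropathy cases is projected. The 54% any-grade rate in Section 1.5, with 51% of those patients having residual neuropathy, comes from single-agent studies in relapsed or refractory disease. It shows that persistence is a foreseeable question, but it does not predict the count here.

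**What to change.** 1. **Protocol.** Reconcile Sections 1.5 and 7.10 and Schedule of Events footnote a with Section 10.3 on the malignancy window. State that new primary malignancy, current grade of unresolved neuropathy, and PML are recorded at the existing post-progression contacts until study closure.
2. **SAP 5.11.1.** Add two by-arm tables. The first covers new primary malignancies over all follow-up, with count and rate per person-year, so that unequal observation time is accounted for. The second covers the outcome of treatment-emergent neuropathy at last contact (resolved, improved, unchanged), with residual grade.

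The cost is wording changes in both documents, three questions at contacts that already take place, slightly longer contacts and a few extra tables. No visit is added.
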